## 2.0 ANALYSIS CONSIDERATIONS

#### 2.1 Analysis Population

#### 2.1.1 **Primary Analysis Population**

The primary analysis population will include patients who have signed an Informed Consent Form (ICF), or for those patients deceased at the time of study screening, all local and national regulatory requirements were met for consent, and at minimum, the Portico delivery system entered his/her vasculature for an attempted Portico ViV implant. Subjects that are enrolled and later determined to be screen failures (those that do not meet all inclusion criteria or meet any exclusion criteria) will not be included in any analysis. Subjects that are enrolled in the Exploratory Arm of the study will not be included in the primary arm of the study.

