Design:	
This is a multi-center, international, single-arm, retrospective data-collection study.
 
The study will enroll subjects who had a documented failed surgical aortic valve bioprosthetic (stenosed, insufficient, or combined etiology) considered to be at increased risk for redo surgical aortic valve replacement (SAVR) surgery that underwent an attempted Portico™ TAVR in any SAVR, referred to here as valve-in-valve (ViV).

	
To participate in this study, patients must have been considered at increased risk for surgical aortic valve replacement and meet eligibility requirements.
 
[REDACTED]
 
[REDACTED]
 
An independent Clinical Events Committee (CEC) will adjudicate all specified safety endpoints according to standardized VARC-2 and VARC-3 criteria; CEC adjudicated adverse events will be presented when reporting study results; source documents will be requested for review by the CEC.
 
An independent echocardiographic Core Laboratory will analyze available echocardiographic exams according to standardized guidelines. Aortic assessments will be based on current American Society of Echocardiography guidelines and VARC definitions.
 
[REDACTED]
 
[REDACTED]

Devices used:	
The devices to be used in this study include the Portico™ transthoracic aortic valve (23, 25, 27, and 29 mm sizes), Portico™ delivery system or the FlexNav™ delivery system, and the Portico loading system or the FlexNav loading system. Each has received approval from the Therapeutic Goods Administration (TGA) in Australia and CE Mark approval in Europe.

Study Population for the Primary Analysis Study Arm:	
A patient becomes a subject in the study once he/she has been fully informed about the study, has agreed to participate and has signed and dated the Informed Consent Form (ICF).
 
For deceased patients, all institutional/local legal and regulatory requirements for enrollment and use of the patient's medical records must be met prior to enrollment and data collection.
 
Patients must meet all inclusion and none of the exclusion criteria during the screening assessment and must have undergone an attempted ViV procedure, defined by the Portico™ or FlexNav™ delivery systems entering his/her body.

Inclusion Criteria

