### 3.2.2 Indication for Use

The Portico™ TAVI system includes the Portico valve, the Portico loading system, Portico delivery system, the FlexNav™ delivery system, and the FlexNav loading system. The Portico system evaluated in this data-collection study will include the following:

- The Portico valve is indicated for transcatheter delivery in patients with symptomatic severe native aortic stenosis who are considered at high or extreme surgical risk.
- The Portico delivery system is indicated for transfemoral or subclavian/axillary access delivery of the Portico valve.
- The Portico loading system is indicated for loading the Portico valve.
- The FlexNav delivery system is indicated for transfemoral or subclavian/axillary delivery of the Portico valve.
- The FlexNav loading system is indicated for loading the Portico valve.

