### **7 ELIGIBILITY CRITERIA**

#### **7.1 Inclusion Criteria**

1. Subject had a degenerated surgical aortic bioprosthetic valve with severe aortic stenosis, severe regurgitation, or a combination of at least moderate stenosis with at least moderate regurgitation per EAPCI-ESC-EACTS standardized criteria.
2. Surgical bioprosthetic true inner diameter (true ID) was  $\geq 19$  mm and  $\leq 27$  mm and was confirmed by either CT or confirmed by the Valve in Valve Aortic App. Refer to the PCR website <https://www.pcronline.com/PCR-Publications/PCR-mobile-apps/Valve-in-Valve-Aortic-app> Note: if CT was contraindicated and/or not possible to be obtained, a transesophageal echocardiogram (TEE) will be accepted for sizing.
3. Prior to Portico ViV procedure, the patient was deemed at increased risk for surgery to replace the surgical aortic bioprosthetic valve.
4. Subject provided written informed consent prior to performing data collection for study specific visits. For patients that are deceased at the time of enrollment, all institutional/local legal and regulatory requirements for consent must be met prior to enrollment and data collection.
5. Subject is  $\geq 18$  years of age or legal age in host country at the time of consent.
6. Prior to the Portico ViV index procedure, the subject had New York Heart Association (NYHA) class II, III, or IV.
7. Subject had a minimum vessel diameter of 6.0 mm for Portico™ delivery system access or a minimum of 5.0 mm for the FlexNav™ delivery system.
8. Subject had the Portico or FlexNav delivery system enter their vasculature with the intent of replacing a failed aortic bioprosthetic valve.

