**Figure 3: Flowchart of Screening and Enrollment**

### 8.1 Point of Enrollment

Subjects will be considered enrolled into the study after completing the following:

- Signed Informed Consent is obtained (as applicable from the patient, legally authorized representative, or next of kin)
- The subject met all of the inclusion and none of the exclusion criteria for one of the study arms.
- Subject had the Portico™ or FlexNav™ delivery system enter his/her vasculature.
- If the subject is deceased, then all local and national requirements for consenting and/or enrollment must be met prior to enrollment and data collection in the study database.

If a patient is enrolled but then subsequently is found to not meet all eligibility criteria, the patient would be excluded and a Protocol Deviation CRF would be completed for not meeting eligibility. Patients who are deemed screening failures are not considered enrolled and are not part of the study analysis population.

The Principal Investigator or delegated study personnel will record enrollment information (name of the study, date of consent and inclusion/exclusion information) in the medical records and the screening/consent study database forms within one week of consenting. The Principal Investigator must document in the enrollment note that the patient met eligibility criteria and was deemed to be at increased risk for surgery to replace the original failed aortic surgical bioprosthetic valve.

Notification of subject enrollment to the Sponsor is considered to have occurred once the patient met all eligibility criteria, the required consent process and forms were completed (with documentation of enrollment in the medical records), and when the screening/consent study database forms have been completed.

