#### **9.4 Subject Study Completion**

Subject participation in the study will conclude when:

1. The subject completes the 5-year data collection time point.
2. When consent is withdrawn (by the subject or legal authorized representative).
3. When the subject is deceased at the time of enrollment or dies during the study, their study completion will occur after their last study follow-up was available, including details of what led up to death and the cause of death.
4. When the subject is lost to follow-up, their study completion will occur after their last study follow-up.
5. For subject's where the Portico delivery system entered their body but was not successfully implanted, they will complete the study after 30 days from the attempted procedure.

Upon completion of subject participation in this data-collection study, the subject will continue to receive follow-up as per standard of care.

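### SAP 2.1.1 names only the Portico delivery system, so applied as written it leaves FlexNav-only subjects, whom the protocol enrols, out of both primary denominators

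*SAP*

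**What the plan says.** **SAP.** Section 2.1.1 asks for consent (or the local equivalent for deceased patients) and that, at minimum, "the Portico delivery system entered his/her vasculature for an attempted Portico ViV implant". It then removes later-identified screen failures and the exploratory arm. The public text of the SAP does not contain the word FlexNav. Sections 2.3.1.1 (safety) and 2.3.1.2 (performance) each refer back to 2.1.1 for their population.

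**Protocol, who is in the study.** The synopsis has an attempted procedure "defined by the Portico™ or FlexNav™ delivery systems entering his/her body". Inclusion criterion 8 in 7.1 reads "Subject had the Portico or FlexNav delivery system enter their vasculature with the intent of replacing a failed aortic bioprosthetic valve". Section 8.1 repeats it as a condition of enrolment: "Subject had the Portico™ or FlexNav™ delivery system enter his/her vasculature". Section 12.1 puts enrolled subjects in the analysis population, sets the exploratory arm apart, and makes no distinction by delivery system.

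**Protocol, the devices.** Section 3.2.2 lists the components of the overall TAVI system separately, among them the "Portico delivery system, the FlexNav™ delivery system, and the FlexNav loading system". Table 2 gives the two delivery systems different model numbers, and inclusion criterion 7 gives them different minimum vessel diameters: 6.0 mm for Portico and 5.0 mm for FlexNav.

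**Protocol, unsuccessful implants.** The 30-day completion rule in 9.4 item 5 covers subjects where "the Portico delivery system entered their body but was not successfully implanted". Section 11.6.1 is worded in the same narrow way.

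**The concern.** The SAP fixes the denominator of both primary endpoints, and its device condition is narrower than the protocol's enrolment condition. In the protocol's own vocabulary the Portico delivery system is a particular product, so a programmer who follows 2.1.1 to the letter would leave out anyone treated only with FlexNav. Three things would follow.

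- The primary results would describe a smaller population than the one the protocol says will be analysed.
- The omitted group need not resemble the rest. Subjects with access vessels of at least 5.0 mm but under 6.0 mm can enter the study only through FlexNav, and major vascular complications are a component of the safety composite.
- SAP 3.2 summarises adverse events for all enrolled subjects, and CEC-adjudicated events for all with an implant attempt. FlexNav subjects could therefore appear in the event tables while missing from the primary rates.

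The data are retrospective, so many outcomes exist before the analysis is run. If the reading of 2.1.1 is settled only then, the sponsor is open to the charge that the population was chosen with results in view.

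**Working it through.** The documents give no derived sample size, power or test for this point (SAP 2.10 states that no hypothesis is tested), so there is no plan figure to reproduce. The check is a comparison of texts, followed by an illustration of size.

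**Step 1. Device condition, place by place.**

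| Place | Delivery system named |
|---|---|
| Protocol synopsis, study population | Portico or FlexNav |
| Protocol 7.1 item 8 | Portico or FlexNav |
| Protocol 8 and 8.1 | Portico or FlexNav |
| Protocol 12.1 | none; all enrolled primary-arm subjects |
| SAP 2.1.1 | Portico only |
| Protocol 9.4 item 5 and 11.6.1 | Portico only |

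**Step 2. Is the Portico delivery system a generic term?** Protocol Table 2 lists it as PRT-DS-TF/18F and 19F, and FlexNav as FNAV-DS-SM and FNAV-DS-LG. Section 3.2.2 gives each its own indication statement. Where the protocol wants an umbrella term it uses the Portico TAVI system. Under these definitions the SAP phrase denotes one of two products.

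**Step 3. Who is left out on a literal reading?** Subjects in whom only FlexNav was used. A subject in whom both systems were used still meets 2.1.1. With criterion 7 at 6.0 mm and 5.0 mm, everyone with an access vessel of at least 5.0 mm but under 6.0 mm is in the FlexNav group.

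**Step 4. Illustrative size.** SAP 1.3 gives a ceiling of 100 subjects for the primary population, and SAP 2.3.1.1 specifies Clopper–Pearson. The FlexNav-only share *f* and the event rate are not in the documents; both are assumed here. With n = 100(1 − *f*) and x events, the 95% limits are the 0.025 quantile of Beta(x, n − x + 1) and the 0.975 quantile of Beta(x + 1, n − x).

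| Assumed *f* | n | x at 10% | 95% interval | Width (points) |
|---|---|---|---|---|
| 0% | 100 | 10 | 4.9–17.6% | 12.7 |
| 20% | 80 | 8 | 4.4–18.8% | 14.4 |
| 40% | 60 | 6 | 3.8–20.5% | 16.7 |
| 60% | 40 | 4 | 2.8–23.7% | 20.9 |

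Widths are differences of the rounded limits. Other event rates give the same pattern. At 8%, the interval goes from 3.5–15.2% (8/100) to 2.2–19.2% (4/50). At 12%, it goes from 6.4–20.0% (12/100) to 4.5–24.3% (6/50).

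These rows hold the event rate fixed, so they show only the loss of precision. They say nothing about bias, because no event rate by delivery system is given.

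**The case against.** The best case for the SAP is that nobody would read it this way.

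- The words at minimum in 2.1.1 set how far the procedure must have gone (entry, not a completed implant). They do not select a device.
- The same paragraph lists its exclusions, and FlexNav is not among them.
- SAP 1.3 requires all eligibility criteria to be met, which brings in criterion 8. SAP 2.3.1.1 and 2.3.1.2 speak of subjects enrolled in the study, and enrolment includes FlexNav.
- Protocol 9.4 and 11.6.1 use the narrow phrase loosely, which suggests shorthand.
- With no hypothesis test, no decision threshold depends on N.

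Most of this stands as evidence of intent: the omission looks like a slip, and actual exclusion of FlexNav subjects is unlikely. It does not make 2.1.1 correct. The references to enrolled subjects point back to 2.1.1 itself, and the conflict with protocol 12.1 remains.

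Four stronger readings may tempt a reader, and the documents do not support them.

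1. *The sponsor chose to exclude FlexNav.* Nothing in either document says so.
2. *Every FlexNav subject is dropped.* Subjects in whom both systems were used still qualify.
3. *The vascular-complication rate changes.* It may, but neither a change nor its direction can be shown.
4. *A failed FlexNav attempt has no follow-up rule.* Item 5 of 9.4 is an exception to general completion rules. Read literally, a failed FlexNav attempt falls under items 1 to 4, and safety surveillance continues under 11.6. The literal consequence is unequal follow-up by delivery system, not absent follow-up.

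**Conclusion.** The point holds as a conflict between the two documents in the definition of the primary population. Followed exactly, SAP 2.1.1 gives a denominator for both primary endpoints that omits FlexNav-only subjects, contrary to protocol 7.1 item 8, 8.1 and 12.1. It is probably a drafting slip and should be corrected before the analysis.

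The size is unknown. It depends on the FlexNav-only share, which could be zero, in which case nothing changes. The intervals above rest on assumed shares, an assumed event rate and the ceiling of 100, and are illustrative only. A shift in the safety estimate is possible, because the smaller-vessel subjects lie wholly within the omitted group, but it is not demonstrated.

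The wording of protocol 9.4 item 5 and 11.6.1 is a separate, related inconsistency. It bears on how long unsuccessful FlexNav attempts are followed and hence on when they are censored in the 1-year Kaplan–Meier analysis.

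**What to change.** In SAP 2.1.1, insert *or FlexNav* after *Portico* where the delivery system is named, so that the condition matches protocol 7.1 item 8 and 8.1. Leave the rest of the sentence as it is. The primary population then agrees with protocol enrolment on the device condition, no figure in either document changes, and no new data are needed. The cost is one phrase in a SAP revision, best made and dated before the dataset is locked.

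Separately, the sponsor should reconcile protocol 9.4 item 5 and 11.6.1 with the enrolment definition and state which subjects the 30-day rule covers. This is not purely editorial, since the answer determines follow-up for unsuccessful FlexNav attempts. It is for the sponsor to decide, and the SAP should then say how such subjects enter the 1-year analysis.

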## 8 SUBJECT ENROLLMENT

Patients must first meet all inclusion criteria and none of the exclusion criteria. Patients must also have had the Portico™ or FlexNav™ delivery system enter their body with the intent to implant the Portico transcatheter aortic valve via ViV procedure. In order for patients to be enrolled as study subjects, the above must be met and the subject (or legally authorized representative/next of kin) must sign the approved study ICF and any required forms designated by the study site/local/national authorities, based on geographic regulations. Patients deceased at the time of study screening may be enrolled per local and national regulations. The enrollment process is outlined below in **Figure 3**.

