## 11.6 Adverse Event and Device Deficiency/Device Malfunction Reporting

Safety surveillance and reporting starts as soon as the patient met all enrollment requirements for the study. Adverse events will not be collected for screen failure subjects. Safety surveillance and reporting will continue until sites perform the last follow-up visit, the subject concludes participation in the clinical investigation, or the subject withdraws from the clinical investigation. Sites will collect all adverse event data, including deaths and device deficiency data throughout the period defined above and will report these events to the Sponsor on a CRF. Sites should update additional information regarding an adverse event on the appropriate CRF.

Unchanged, chronic, non-worsening or pre-existing conditions are not AEs and should not be reported.

The Sponsor will provide an offline form to allow the investigator to report SAEs in the event the entry cannot be made in the electronic data capture (EDC) system. This does not replace the EDC reporting system. Sites must still enter all information in the EDC system as soon as feasible.

Non-cardiac related laboratory values collected in the study that are abnormal will not be considered AEs unless:

1. the investigator determined that the value is clinically significant,
2. the abnormal lab value required intervention, or
3. the abnormal lab value required subject withdrawal from the clinical investigation.

Clinical Site	Reporting timelines
All Sites	
Sites must report SAE and Device Deficiency/Device Malfunction events to the Sponsor no later than 3 calendar days from the day the site personnel became aware of the event or as per the investigative site's local requirements, if the requirement is more stringent than those outlined.
 
Note: SAEs that occur prior to the subject's Portico ViV procedure are not required to be submitted/reported (refer to Table 3).

Sites must record the date the site staff became aware that the event met the criteria of an SAE in the source document. The Investigator will further report the SAE to the local EC according to the institution's EC reporting requirements.

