### 12.1 Analysis Population

Subjects who are enrolled in the study will be included in the analysis population. Subjects that are enrolled in the Exploratory Arm of the study will not be included in the primary arm of the study.

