#### 2.12 Sensitivity Analysis

For the primary safety endpoint and performance endpoint, a sensitivity analysis will be conducted including all CEC adjudicated component events regardless of relationship to COVID-19 to assess the impact of the pandemic. Sensitivity analysis will also be conducted including all CEC adjudicated VARC-2 events and VARC-3 events regardless to COVID-19 to assess the impact of the pandemic.

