#### 3.2 Adverse Events

All adverse events, serious adverse events (SAEs), unanticipated serious adverse device effects (USADEs) will be summarized for all subjects who enrolled in this trial in terms the number of events and the number of subjects, as well as the percentage of subjects with events per AE term if relevant for the specific analysis. All CEC adjudicated adverse events will also be summarized for all subjects who underwent an implant attempt in terms the number of events, the percentage of subjects with events. Moreover, COVID-19 related AEs will be summarized in terms of number of events and the number of subjects, as well as the percentage of subjects with events per AE term if relevant for the specific analysis.

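### SAP 2.1.1 drops enrolled subjects later found ineligible from every analysis, and no planned analysis shows the primary endpoints with them included

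*SAP*

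**What the plan says.** SAP 2.1.1 defines the primary analysis population by valid consent (or, for deceased patients, by meeting local and national requirements) and by entry of the Portico delivery system into the vasculature. It then removes enrolled subjects later classed as screen failures: "those that do not meet all inclusion criteria or meet any exclusion criteria) will not be included in any analysis". Protocol 8.1 has the same effect: "If a patient is enrolled but then subsequently is found to not meet all eligibility criteria, the patient would be excluded", with a deviation form completed.

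Other sections fit this rule less well:

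- Protocol 12.1: "Subjects who are enrolled in the study will be included in the analysis population". It makes no exception for subjects later found ineligible.
- Protocol 8.1: "Patients who are deemed screening failures are not considered enrolled and are not part of the study analysis population". The SAP, by contrast, applies the term screen failure to people who were enrolled.
- SAP 3.2: adverse events are "summarized for all subjects who enrolled in this trial", and a second sentence summarises all CEC-adjudicated events in everyone in whom an implant was attempted.
- Protocol 12.3 and SAP 2.4: further subjects with an attempted implant may be analysed.
- Protocol 11.6: "Adverse events will not be collected for screen failure subjects".

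The sensitivity analyses in SAP 2.12 concern COVID-19 ("a sensitivity analysis will be conducted including all CEC adjudicated component events regardless of relationship to COVID-19") and the VARC-2 and VARC-3 event definitions. The only subgroup, in SAP 2.7, is subjects treated with adjunctive techniques.

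**The concern.** Both the baseline record and the outcome may exist before anyone decides whether a subject was eligible, and SAP 2.6 sets the database lock around completion of 1-year follow-up. A decision to remove a subject can therefore be taken with the outcome in view. Some criteria in protocol 7.1 and 7.2 call for judgement or lie close to the procedure: increased risk for redo surgery, haemodynamic instability at the procedure, and vascular disease that made access impossible. A complicated case could be re-read against one of these.

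The study tests no hypothesis (SAP 2.10), so the two estimated rates and their precision are the result. If subjects are removed after enrolment and the endpoints are never shown with them included, a reader cannot tell whether the removals moved either rate.

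**Working it through.** **Is there a planned analysis that adds the removed subjects back?**

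| Section | What it varies | Restores removed subjects to the primary endpoints? |
|---|---|---|
| SAP 2.12, first analysis | COVID-19 relatedness of events | No |
| SAP 2.12, second analysis | VARC-2 and VARC-3 events | No |
| SAP 2.7 | Adjunctive techniques | No |
| SAP 2.9 | Site differences at the 0.15 level | No |
| SAP 3.4 | Count of protocol deviations | No; shows how many, not their outcomes |
| SAP 3.2, second sentence | Adjudicated events after any implant attempt | Possibly as event counts, but in conflict with SAP 2.1.1, and not as the primary composites |

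**How large could the effect be?** The documents give no expected event rate or removal rate, so there is no figure of the plan to reproduce. Inputs:

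- N = 100, the maximum for the primary population (SAP 1.3).
- Events X = 8 at 30 days and X = 14 at 1 year: assumed. They lie near the 8.4% and 14.2% (100% − 85.8%) mortality of the registry of other manufacturers' valves in protocol 2.1. The composite rates here would differ.
- Removed k = 3, with e events among them: assumed. The extremes are e = 3 and e = 0.

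Rate after removal = (X − e)/(N − k).

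*30 days, Clopper-Pearson 95% interval (the planned method):*

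- None removed: 8/100 = 8.0% (3.5% to 15.2%)
- Three removed, all with events: 5/97 = 5.2% (1.7% to 11.6%)
- Three removed, none with events: 8/97 = 8.2% (3.6% to 15.6%)

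*1 year, Kaplan-Meier with Greenwood standard error.* Without censoring (assumed), the standard error is √(p(1 − p)/n). The SAP does not name an interval for this endpoint; a linear one, p ± 1.96 × SE, is used here.

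- None removed: 14/100 = 14.0%, SE 3.5 points (7.2% to 20.8%)
- Three removed, all with events: 11/97 = 11.3%, SE 3.2 points (5.0% to 17.7%)
- Three removed, none with events: 14/97 = 14.4%, SE 3.6 points (7.4% to 21.4%)

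The largest shifts are 2.8 points at 30 days (8.0 − 5.2) and 2.7 points at 1 year (14.0 − 11.3), both downward. The largest upward shifts are 0.2 and 0.4 points. Every shifted estimate lies inside the interval with no removals.

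**The case against.** The plan has real safeguards. Protocol 4.3 screens all Portico valve-in-valve cases whatever the result. Protocol 8.1 requires enrolment and eligibility information to be recorded within a week of consent, with an investigator's note that the criteria were met. Protocol 14.6 bars waivers, protocol 15.4 provides source review and central monitoring, and SAP 3.4 counts deviations. Many criteria are recorded measurements, such as ejection fraction, creatinine and blood counts. A subject who fails only the true inner diameter limits could be analysed in the exploratory arm. All of this narrows the room for outcome-dependent removal, but none of it shows the effect of removals on the endpoints.

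The illustration is also an extreme: all three removed subjects have events, or none does. That is fair. The shifts are still worth showing, because a sampling interval does not describe selection.

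A reader might go further in three ways that the documents do not support.

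- *That outcomes of removed subjects are hidden.* SAP 3.2 summarises adjudicated events after any implant attempt, and SAP 2.4 allows further attempted-implant subjects to be analysed. The fault is that these sections and SAP 2.1.1 do not agree.
- *That the two documents disagree on whether ineligible subjects are excluded.* SAP 2.1.1 and protocol 8.1 both exclude them; the differing use of enrolled and screen failure is mostly terminology. In protocol 11.6, surveillance starts once enrolment requirements are met, so screen failure there most naturally means before enrolment. It needs stating only because the SAP uses the term for enrolled subjects too.
- *That mortality is understated because "Patients deceased at the time of study screening may be enrolled per local and national regulations".* No section shows a site that cannot enrol deceased patients, and protocol 8 foresees consent by a representative or next of kin. Survivors must also consent, and those who do not are missing too. Take 1-year mortality of 14.2%, all those deaths before screening, and 25% of them not enrollable (all assumed for illustration). The observed rate is 0.142 × 0.75 / [0.142 × 0.75 + 0.858 × (1 − g)], where g is the share of survivors not enrolled. It is 12.1% at g = 10%, 14.2% at g = 25% and 15.1% at g = 30%. The sign is open, so no downward figure should be stated.

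**Conclusion.** The point stands in a limited form. SAP 2.1.1 removes enrolled subjects from every analysis on a judgement that may be made after the outcome is known. No planned analysis shows either primary endpoint with them included, and the rule cannot be squared with the implant-attempt population in SAP 3.2. The documents do not show that removals will depend on outcome, how many there will be, or which way they would push the rates. Under the assumed 3 removals in 100, the effect ranges from 2.8 points down to 0.2 points up at 30 days, and from 2.7 points down to 0.4 points up at 1 year, within sampling error. This should be settled before database lock, while data on removed subjects can still be secured. It does not call the eligible-only primary analysis into question.

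**What to change.** 1. In SAP 2.1.1, limit the exclusion of enrolled subjects later found ineligible to the primary analysis, and name both the Portico and FlexNav delivery systems, to match protocol 7.1 and 8.1.
2. Add one sensitivity analysis of both primary endpoints to SAP 2.12, with the planned estimators (Clopper-Pearson at 30 days; Kaplan-Meier with Greenwood errors at 1 year). Its population is all validly consented or lawfully enrolled primary-arm subjects (true inner diameter 19 to 27 mm) in whom either delivery system entered the vasculature.
3. List removed subjects by criterion failed, date of decision and outcome.
4. Reconcile SAP 2.1.1 with SAP 3.2. State that the exemption in protocol 11.6 covers only screen failures before enrolment, so that data on removed subjects are kept.

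The cost is one table, one listing, SAP wording and a clarification in protocol 11.6. Outcomes of removed subjects may be incomplete, and the table should say so.

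Optional and of lower priority: report identified versus enrolled valve-in-valve cases by site, with reasons for non-enrolment and vital status where permitted. This would let a reader judge selection by survival in either direction. An analysis restricted to sites that can enrol deceased patients, or a blinded eligibility reviewer, is not asked for: the plan has neither the data nor the staff for them.
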